### **3.6.10 Disease Evaluations**

#### **3.6.10.1 Asthma Exacerbations**

Asthma exacerbation data will be collected through Study Day 168. For the purpose of this study, an asthma exacerbation (relapse or de novo) is defined as either 1) an increase of asthma symptoms (cough, wheeze, chest tightness, and/or shortness of breath) that does not resolve within 2 hours after the use of rescue albuterol or corticosteroids and requires an unscheduled medical visit or 2) during a scheduled study visit, the subject has acute worsening of asthma symptoms and a reduction of  $\geq 20\%$  in PEF or FEV1, which in the opinion of the investigator requires treatment with systemic corticosteroids.

An exacerbation event will be considered resolved if the subject's acute asthma symptoms diminish or PEF or FEV1 return to  $> 80\%$  of baseline for  $> 7$  days after completion of oral steroid burst therapy.

The following information will be collected for each asthma exacerbation:

- Date of onset
- Date of visit to healthcare provider or ED
- Treatment
- Resolution date

In this study, 2 aspects of asthma exacerbations will be collected: (1) number of subjects with at least one exacerbation during the study, and (2) number of exacerbations per subject in each treatment group.

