## **5 Statistical Considerations**

### **5.1 General Considerations**

All data will be provided in data listings sorted by treatment groups (MEDI-563 0.3 mg/kg, MEDI-563 1.0 mg/kg, or placebo), and visit number. Summary data will be presented in tabular format by treatment groups. Categorical data will be summarized by the number and percentage of subjects in each category. Continuous variables will be summarized by descriptive statistics including N, mean, standard deviation, median, and range. Statistical hypothesis testing, if appropriate, will be performed for the primary endpoint with a 2-sided test.

A comprehensive statistical analysis plan will be developed and approved prior to the database lock.

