### 5.4 Primary Endpoint

The primary objective of this study is to evaluate the effect of two IV dose regimens of MEDI-563 (0.3 and 1.0 mg/kg) on the proportion of subjects with asthma exacerbations (relapsed or de novo) at Week 12 in adult subjects who required an urgent healthcare visit for treatment of an acute asthma exacerbation. The formula that will be used to evaluate the proportion of subjects with asthma exacerbations in the combined MEDI-563 treatment groups at Week 12 will be as follows:

- $$\frac{\text{(Number of subjects with at least one asthma exacerbation in the combined MEDI-563 treatment groups [0.3 and 1.0 mg/kg] at Week 12)}}{\text{(Number of total evaluable subjects in the combined MEDI-563 treatment groups [0.3 and 1.0 mg/kg] at Week 12)}}$$

The Fisher’s exact test will be performed for testing the differences in proportion of subjects with asthma exacerbations at Week 12 between the combined MEDI-563 treatment groups and the placebo group at an alpha level of 0.05.

The number of asthma exacerbations at Week 12 for each MEDI-563 treatment group (0.3 and 1.0 mg/kg) versus placebo will also be reported. The Fisher’s exact test may be performed for testing this endpoint.

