### **5.5.2 Effect of MEDI-563 on the Proportion of Subjects with Asthma Exacerbations at Week 4**

The formula in Section 5.4 will be used to explore the differences in the proportion of subjects with asthma exacerbations in each MEDI-563 treatment group (0.3 and 1.0 mg/kg) versus placebo and for the combined MEDI-563 treatment groups versus placebo at Week 4. The Fisher's exact test may be performed for testing this endpoint.

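### Section 5.4 and the abstract attach Fisher's exact test to the number of exacerbations per dose at Week 12; the test fits only the number of subjects with at least one exacerbation

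*Protocol*

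**What the plan says.** Section 5.4 of the protocol defines the primary endpoint as a proportion: evaluable subjects with at least one exacerbation by Week 12, divided by all evaluable subjects. For the pooled MEDI-563 groups against placebo, Fisher's "exact test will be performed for testing the differences in proportion of subjects with asthma exacerbations at Week 12".

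The next paragraph turns to the individual doses and changes the quantity: "The number of asthma exacerbations at Week 12 for each MEDI-563 treatment group (0.3 and 1.0 mg/kg) versus placebo will also be reported". It then says that Fisher's "exact test may be performed for testing this endpoint". The abstract (Assessment of Endpoints) has the same two sentences.

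Section 3.6.10.1 says that two aspects of exacerbations are collected: "1) number of subjects with at least one exacerbation during the study, and (2) number of exacerbations per subject in each treatment group".

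For Week 4, Section 5.5.2 frames the per-dose comparison as the "proportion of subjects with asthma exacerbations in each MEDI-563 treatment group (0.3 and 1.0 mg/kg) versus placebo". Section 5.5.3 does the same for Week 24.

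**The concern.** A 2x2 Fisher test needs one yes/no result per subject. The number of exacerbations does not supply that: a subject can contribute none, one or several. Section 3.6.10.1 allows for repeats, since it defines when an event has resolved and collects a per-subject count. In the Week 12 per-dose sentence, therefore, the quantity and the test do not match. If subjects were meant, the quantity is misnamed; if events were meant, the test is wrong.

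At stake is the only formal comparison that the protocol names for the separate doses at the primary time point. An analyst following the text literally would either be unable to build the table or would build one whose nominal 5% level does not hold.

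**Working it through.** **Inputs from the protocol.** Each dose group has 36 subjects (Table 3.4.2-1). Placebo is 18 + 18 = 36 when pooled across the two arms, as in Section 5.2.1. The placebo proportion with an exacerbation is 60%, and halving it gives 30% (Section 5.2.1). Alpha is 0.05 (Section 5.4), 2-sided (Section 5.1).

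**Assumptions, because the protocol gives no event rate per subject or dispersion.** Counts per subject are Poisson (dispersion k = 0) or negative binomial with variance μ + kμ², for k up to 2. The mean μ is set so that the stated proportion p has at least one event:
- k = 0: μ = −ln(1 − p)
- k > 0: μ = [(1 − p)^(−k) − 1] / k

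**Step 1: reproduce the plan's own figure.** Exact enumeration of the 2-sided Fisher test on subjects, 36 at 60% versus 72 at 30%, gives power of 81.1%, against the stated 80%. The continuity-corrected formula returns the stated 36 placebo subjects, and also the 43, 49 and 57 of Table 5.2.2-1. All these figures take the subject as the unit.

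**Step 2: can the table be formed from event totals?** The cells would be events and 36 − events in each arm, which fails once an arm has more than 36 events. The expected total per arm is 36μ. With no treatment difference and F the distribution function of an arm's total, the chance that at least one arm fails is 1 − F(36)². At p = 60%:

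| k | μ | 36μ | at least one arm above 36 |
|---|---|---|---|
| 0 | 0.92 | 33.0 | 46% |
| 0.5 | 1.16 | 41.8 | 93% |
| 1 | 1.50 | 54.0 | 99.7% |
| 2 | 2.62 | 94.5 | 100% |

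**Step 3: what is the size where the table can be formed?** At a common p = 30% the totals rarely exceed 36 (at most 1.4% of trials, at k = 2). The size is the sum of P(a)P(b) over all pairs of totals (a, b), each at most 36, for which Fisher's p-value is 0.05 or less, divided by F(36)²:

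| k | size at nominal 5% |
|---|---|
| 0 | 7.6% |
| 0.5 | 11.3% |
| 1 | 16.1% |
| 2 | 27.6% |

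The level is exceeded even under Poisson counts. The test takes the variance of a yes/no outcome, about 36p(1 − p) for an arm total, whereas a Poisson total has variance equal to its mean. Overdispersion widens the gap.

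**Step 4: the same test on subjects.** For 36 versus 36, counting subjects with at least one exacerbation, the exact size is 2.6% at a common 60% and 2.8% at a common 30%. Power for 60% versus 30% is 63.6%.

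**The case against.** The strongest reply is that this is a slip of wording. Section 5.4 is headed Primary Endpoint and defines only a proportion of subjects. The sentence permitting Fisher's test recurs in Sections 5.5.2 and 5.5.3, where the quantity is the proportion. Amendment 4 records a change from exacerbation rate to proportion of subjects throughout, so the odd sentence may be one that was not brought into line. This is the likely explanation and it stands. It explains the text but does not correct it: the sentence still names a count that Section 3.6.10.1 distinguishes from the number of subjects.

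The test is also optional, and Section 5.1 says that testing, if appropriate, "will be performed for the primary endpoint with a 2-sided test". That stands too, and it limits the weight of the point. Deferring to the statistical analysis plan does not remove it, because the protocol itself names both the quantity and the test.

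A Fisher-type test on a larger table, classifying subjects by 0, 1, 2 or more events, would keep the subject as the unit and be valid. The protocol describes no such table.

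A reader might infer more than the document supports:
- **That the invalid test is a commitment.** The text only permits it.
- **That dose selection depends on it.** Neither the rationale nor the objectives say that this trial selects a dose.
- **That per-dose Week 12 proportions will be missing.** Section 5.1 calls for numbers and percentages by treatment group, so they would be tabulated. Only a named test on them is lacking.
- **That an error rate from a conditional comparison of event totals measures this plan.** The protocol names no such test.

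**Conclusion.** The point holds as a mismatch between quantity and test in a supportive, optional analysis, most likely a drafting slip. Followed literally, the table cannot be formed in about 46% to 100% of trials at the protocol's 60% placebo proportion, and at 30% the nominal 5% test has size of about 8% to 28%. These figures assume 36 versus 36 with placebo pooled, no true difference, and dispersion between 0 and 2, a range that is not in the protocol. The qualitative conclusion does not depend on overdispersion, since the level already fails under Poisson counts.

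The pooled primary comparison uses the subject as the unit, so it and its stated 80% power are unaffected. It should be corrected, but it does not threaten the trial's main result.

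**What to change.** In Section 5.4 and in the matching sentence of the abstract, replace the quantity with: *the proportion of subjects with at least one asthma exacerbation at Week 12 for each MEDI-563 treatment group (0.3 and 1.0 mg/kg) versus placebo*. Keep Fisher's exact test and label the comparison supportive, since its power is only about 64% for 60% versus 30%. This brings Week 12 into line with Sections 5.5.2 and 5.5.3.

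Report the number of exacerbations per subject descriptively. If it is to be tested, use a count method with the subject as the unit that allows for overdispersion and follow-up time, negative binomial regression being one example, and not Fisher's test. That model is optional and the correction does not depend on it.

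The cost is two sentences of protocol text and matching wording in the statistical analysis plan. Both measures are already collected under Section 3.6.10.1, and the sample size does not change.

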## **5.5 Secondary Endpoints**

### **5.5.1 Safety Assessment**

The safety of MEDI-563 in this subject population is a secondary objective of this study. Adverse events will be summarized categorically by system organ class, preferred term, severity, and relationship to investigational product through Study Day 84. Serious adverse events will be assessed through Study Day 84. Laboratory abnormalities, for tests such as serum CRP, ECP, and IL-6 levels will be evaluated in the MEDI-563 and placebo groups as changes from baseline.

### **5.5.2 Effect of MEDI-563 on the Proportion of Subjects with Asthma Exacerbations at Week 4**

The formula in Section 5.4 will be used to explore the differences in the proportion of subjects with asthma exacerbations in each MEDI-563 treatment group (0.3 and 1.0 mg/kg) versus placebo and for the combined MEDI-563 treatment groups versus placebo at Week 4. The Fisher's exact test may be performed for testing this endpoint.

### **5.5.3 Effect of MEDI-563 on the Proportion of Subjects with Asthma Exacerbations at Week 24**

The formula in Section 5.4 will be used to explore the differences in the proportion of subjects with asthma exacerbations in each MEDI-563 treatment group (0.3 and 1.0 mg/kg) versus placebo and for the combined MEDI-563 treatment groups versus placebo at Week 24. The Fisher's exact test may be performed for testing this endpoint.

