### **5.2 Sample Size and Power Calculations**

#### **5.2.1 Planned Sample Size**

Sample size calculations have been performed for the primary endpoint of proportion of subjects with asthma exacerbations at Week 12 to allow for hypothesis testing. Sample size calculations are based on Fisher's exact test with  $\alpha = 0.05$  (2-sided) for testing the difference between the combined MED-563 treatment groups ( $n=72$ , 0.3 mg/kg and 1.0 mg/kg) and the combined placebo group ( $n=36$ ). Assumptions include: (1) The proportion of placebo subjects with asthma exacerbations at Week 12 is 60% and (2) There will be  $\geq 50\%$

reduction in the proportion of subjects with asthma exacerbations at Week 12 in the combined MEDI-563 (0.3 and 1.0 mg/kg) treatment groups. The sample size may be re-estimated using the proportion of subjects with asthma exacerbations (relapsed or de novo) up to the first interim analysis to preserve the power around 80% if the proportion of subjects with asthma exacerbations is different from the assumptions listed above.

There will be no adjustment on Type 1 error rate for sample size re-estimation in this study. However, the true overall type I error rate will be greater than 0.05 if the multiplicity adjustment is taken into account in the calculation. With 108 evaluable subjects, the statistical power to detect statistically significant differences in the proportion of subjects with asthma exacerbations at Week 12 in the combined MEDI-563 treatment groups and the placebo group will be 80% based on the above assumptions. Power calculations were performed using nQuery Advisor software program Version 6.01.

Table 5.2.1-1 and [Table 5.2.1-2](#) present the probability of observing at least one infrequently occurring event when assuming a range of potential observed event rates and exact binomial 95% confidence intervals to assess the precision of estimates of the event rate for each individual treatment group (n=36) and combined MEDI-563 treatment group (n=72).

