### 5.3 Analysis Populations

All evaluable subjects will be included in the efficacy analyses. All randomized subjects, regardless of whether they are evaluable, will be included in the safety analyses. Missing data will be treated as missing without data imputation.

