## Appendix 6 Summary of Amendments to the Protocol

### Protocol Amendment 1; [REDACTED]

All text revisions resulting from this amendment are incorporated in the body of Protocol Amendment 1. Major changes to the protocol are described below.

- 1) The Study Abstract was updated to be consistent with changes in the body of the protocol.
- 2) The potential number of participating sites was increased from approximately 5 sites in the US to up to 10 sites in North America. This change is to facilitate enrollment.
- 3) The study was shortened to accommodate the ED population. Subjects will only receive one dose of investigational product and be followed for 84 days. This follow-up period is more than 5 half-lives of MEDI-563. In addition, since the primary endpoint of the study is asthma exacerbation rate at Week 12, one dose of investigational product should be adequate to evaluate the differences between treatment groups. Changes were made throughout the protocol to accommodate this change.
- 4) The study visit schedule was changed to accommodate the reduction in study duration. Subjects will be evaluated at the study site on Study Day 0, Study Day 7; Study Day 42; and Study Day 84. Subjects will be contacted by telephone on Study Day 28 and Study Day 63. Based on data from MI-CP158, this schedule is adequate to evaluate safety and efficacy. Changes were made to the study design, study flow diagram, and study schedule.
- 5) The 0.1 mg/kg dose of investigational product was changed to 0.3 mg/kg. This change was made to ensure adequate drug coverage throughout the study period.
- 6) Study objectives 2 (evaluate the effect of MEDI-563 on the time to the first asthma exacerbation after dosing) and 4 (evaluate the effect of MEDI-563 on the asthma exacerbation rate at Week 26) were removed because the reduction in study duration makes them not applicable. The corresponding endpoints were removed from the statistical section.
- 7) Study treatment initiation was changed from prior to being discharged from the hospital or ED to within 7 days of meeting eligibility criteria. This change was made because many subjects wanted more time to think about participating in the study. It should not affect the evaluation of the primary endpoint. This change affected the study design section and concomitant medications (ie, prednisone).
- 8) The following inclusion criteria were changed to facilitate enrollment in the study.

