### Protocol Amendment 3; [REDACTED]

All text revisions resulting from this amendment are incorporated in the body of Protocol Amendment 3. Major changes to the protocol are described below.

- 1) The Study Abstract was updated to be consistent with changes in the body of the protocol.
- 2) Nonclinical section was updated.
- 3) A secondary objective was added to evaluate the effect of MEDI-563 on the asthma exacerbation rate (relapse or de novo) at Week 24. This change was made to gather additional data about asthma exacerbations after treatment with MEDI-563. The change was made in the objectives and in the statistical section.
- 4) Three additional phone contacts were added (Study Day 112, 140, and 168) to assess asthma exacerbations beyond the last study visit on Study Day 84. This change was made to gather data needed for the additional secondary objective listed above. The change was made to the study design and study schedule.
- 5) Study Day 84 was change to Study Day 168 where appropriate throughout the protocol. The only assessments made after Study Day 84 will be for asthma exacerbations.
- 6) Inclusion and Exclusion criterion were clarified as follows:
  - a) Inclusion criterion Number 8 was changed to allow for PEF or spirometry. This change was made because study sites often do PEF, not spirometry as part of the standard of care.
  - b) Inclusion criterion Number 8 was further changed to remove the requirement of at least 30%. This was moved to inclusion criterion Number 14 and is now:  
Investigator has determined the subject is clinically stable and  $FEV_1 \geq 30\%$  predicted prior to dosing with investigational product. This change was made for clarification purposes; subjects must have an  $FEV_1$  of at least 30% predicted on Study Day 0 in order to receive the investigational product.
  - c) Inclusion criterion Number 12 was changed to a normal for an asthmatic population and excludes alternative diagnosis per the investigator.
  - d) Exclusion criterion Number 7 was changed to allow travel outside of the US and Canada as long as it was not to a location where parasite infestations are prevalent within the last year. This change was made for clarification.
  - e) Exclusion criterion Number 21 was clarified. Subjects who had a known exposure to inhaled occupational agents or fumes with an established diagnosis of occupational asthma will be excluded.

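### The Week 24 exacerbation proportion has no stated rule for evaluable subjects who were not assessed through Day 168, and the two most direct readings move it in opposite directions

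*Protocol*

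**What the plan says.** Section 5.5.3 carries the primary-endpoint calculation to Week 24: "The formula in Section 5.4 will be used to explore the differences in the proportion of subjects" with exacerbations, for each dose and for the combined doses against placebo, with an optional Fisher's exact test. The Section 5.4 formula divides subjects with at least one exacerbation by total evaluable subjects. Sections 2.3 and 3.2 define evaluable as dosed and followed according to the protocol through Day 42. No separate evaluability is defined for Week 24.

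Section 5.3 adds two rules: "All evaluable subjects will be included in the efficacy analyses" and "Missing data will be treated as missing without data imputation".

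Follow-up length differed between protocol versions. Appendix 6 records that Amendment 1 cut follow-up to 84 days. Under Amendment 3, "Three additional phone contacts were added (Study Day 112, 140, and 168) to assess asthma exacerbations" after the last site visit, and the Week 24 objective came in with them. The current text follows every subject to Day 168 (Sections 3.6.10.1 and 3.7).

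**The concern.** Evaluability is settled at Day 42, but the Week 24 endpoint needs ascertainment to Day 168. An evaluable subject can therefore have no exacerbation assessment for much of the window. Dropouts after Day 42 are one source. Subjects who completed under Amendments 1 or 2 and were never contacted again would be another.

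The Section 5.4 denominator keeps such subjects, so an unobserved period is scored as event-free and the proportion is too low. The missing-data rule in Section 5.3 could instead remove those whose Week 24 status is unknown. A subject with an event before the last contact already has a known status, so only the event-free would leave and the proportion would be too high.

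At stake is what the Week 24 objective was added to learn: how exacerbations behave beyond Day 84. Scoring some subjects as event-free from Day 84 makes Week 24 resemble Week 12. Section 1.4 reports eosinopenia lasting up to 12 to 16 weeks at the higher Phase 1 doses, so a waning effect by Week 24 is plausible and should not be blurred.

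**Working it through.** **The plan's own figure.** The protocol gives no Week 24 figure. Its only power statement is for Week 12: 36 placebo and 72 MEDI-563 subjects, 60% against 30%, Fisher's exact test "at an alpha level of 0.05", two-sided, with power that "will be 80% based on the above assumptions". Exact enumeration gives 81.1%, so the statement reproduces. It does not bear on Week 24.

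**Inputs.**
- Week 12 proportions p12: 60% placebo and 30% MEDI-563 (Section 5.2.1).
- Week 24 proportions p24: not given. Assuming a constant hazard, p24 = 1 − (1 − p12)². Placebo: 1 − 0.40² = 84%. MEDI-563: 1 − 0.70² = 51%. The true difference is 33 points.
- Share f of evaluable subjects with no assessment after Day 84: not given and possibly zero. Assumed 10%, 20% and 40%, equal in both arms and unrelated to prognosis.

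**Reading A**, all evaluable subjects in the denominator and unobserved time scored as event-free: f·p12 + (1 − f)·p24.

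**Reading B**, event-free subjects without later follow-up dropped and those with an event kept: [f·p12 + (1 − f)·p24] / [1 − f·(1 − p12)].

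Worked at f = 40%:
- A, placebo: 0.4 × 0.60 + 0.6 × 0.84 = 0.744.
- A, MEDI-563: 0.4 × 0.30 + 0.6 × 0.51 = 0.426.
- B, placebo: 0.744 / (1 − 0.4 × 0.40) = 0.744 / 0.84 = 0.886.
- B, MEDI-563: 0.426 / (1 − 0.4 × 0.70) = 0.426 / 0.72 = 0.592.

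| f | A: placebo / MEDI-563 | A: difference | B: placebo / MEDI-563 | B: difference |
|---|---|---|---|---|
| 0% | 84.0 / 51.0 | 33.0 | 84.0 / 51.0 | 33.0 |
| 10% | 81.6 / 48.9 | 32.7 | 85.0 / 52.6 | 32.4 |
| 20% | 79.2 / 46.8 | 32.4 | 86.1 / 54.4 | 31.7 |
| 40% | 74.4 / 42.6 | 31.8 | 88.6 / 59.2 | 29.4 |

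At f = 40% the choice of reading alone moves the placebo proportion by 88.6 − 74.4 = 14.2 points and the MEDI-563 proportion by 59.2 − 42.6 = 16.6 points. The contrast moves far less.

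**If the effect wanes.** Assume 70% and 45% at Week 24, a true difference of 25 points. Reading A gives 68 − 42 = 26 points at f = 20% and 66 − 39 = 27 points at f = 40%, so it slightly overstates the late effect. Reading B gives 25.1 and 24.4. The direction of the error in the contrast therefore depends on the true time course.

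**The case against.** The strongest reply is that nothing shows anyone is affected by the change in follow-up. Appendix 6 explains an Amendment 1 change by saying that "many subjects wanted more time to think about participating in the study". That suggests recruitment had been attempted, but not that anyone was dosed and completed Day 84 before Amendment 3. The amendment dates are redacted, and subjects dosed shortly before Amendment 3 could still have been inside the 168-day window. Not every earlier version ran for 84 days, since Amendment 1 removed a Week 26 objective. All of this stands. A reader might infer that 84-day completers are in the Week 24 denominator; the documents do not establish it. Later dropouts fall under the same unclear rule, though their number is unknown too.

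A reader might also infer that the plan is biased however it is read. That is not supported. Section 5.3 can be taken to exclude everyone without Week 24 follow-up, whatever happened earlier, and for subjects cut off only by their protocol version this avoids the bias. The text allows that reading but does not choose it.

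It can be said that this belongs in the statistical analysis plan and that using an amendment log against current text is unfair. The first has some force for an exploratory endpoint, but the protocol does fix a formula and population for Week 24, and that choice is open to comment. On the second, the log serves only as evidence that follow-up length differed between versions.

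Finally, Amendment 1 dropped time to first exacerbation as an objective. A Kaplan-Meier estimate of the Week 24 proportion does not restore it; the target remains a proportion.

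**Conclusion.** The point holds as an unresolved denominator rule for Week 24. Followed literally, Sections 5.3, 5.4 and 5.5.3 score unobserved time as event-free. Removing only the event-free biases the proportions upward, and the protocol does not say which rule applies.

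Under the assumed constant hazards and 10% to 40% affected, arm proportions are understated by about 2 to 10 points or overstated by about 1 to 8 points. The difference falls from 33 points to between 32.7 and 31.8, or between 32.4 and 29.4. With nobody affected there is no error. These figures rest on an assumed share, equal in both arms, and on assumed Week 24 proportions.

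The consequence is minor. Week 24 is an exploratory secondary comparison with an optional test. The Week 12 primary analysis and the sample size of 108 do not depend on it.

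**What to change.** In Section 5.5.3, state one of the following:

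1. Estimate the Week 24 proportion in each group by Kaplan-Meier for first exacerbation, censoring each subject at the last contact at which exacerbations were assessed. This handles both short follow-up by protocol version and later dropout, provided dropout is unrelated to exacerbation risk. If a test is wanted, it should compare the Kaplan-Meier estimates in place of Fisher's exact test.
2. Restrict the Week 24 denominator to subjects enrolled or re-consented under follow-up to Day 168, whether or not they had an earlier event. This keeps the simple proportion and Fisher's test but does not handle later dropouts, who would still need a stated rule.

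In either case, report the number of subjects by length of planned follow-up.

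The cost is wording. Onset dates are already collected under Section 3.6.10.1, and the contacts are scheduled. The small downside is that fewer subjects inform Week 24 than Week 12: under option 2, about 32 placebo and 65 MEDI-563 subjects if 10% are affected, 29 and 58 at 20%, and 22 and 43 at 40% (36 and 72 multiplied by 1 − f, rounded).
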